10.5 Method of Assigning Subjects to Treatment

Subjects who meet all inclusion and exclusion criteria will be centrally randomized 1:1 to receive either no treatment or 1.6 mg Ta1 in 1 mL doses to be delivered twice weekly after dialysis (with treatment days separated by at least 2 full days without Ta1 injection), via SC injection for 8 weeks, in accordance with a computer-generated randomization schedule prepared by the Inova Biostatistical core.

Randomization will be stratified by dialysis site.

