15 STATISTICAL ANALYSIS

15.1 Sample size justification

It has been speculated that infection rates may be as high as 40% in the general population and for those over the age of 60 years, particularly those with underlying comorbidities, the rate may be higher. Further, patients who receive dialysis two or three times weekly at dialysis centers are more likely to be exposed to virus than the general elderly population. In as much as there are no existing data demonstrating the effects of Ta1 in prevention of COVID-19 infection, in this pilot project we have elected to sample 240 subjects, anticipating that 40 subjects will drop off study for any of a number of reasons. That will leave ~200 enrolled subjects with complete data availability. We justify the choice of sample size below.

Clinical Study Protocol: Ta1 to Prevent COVID-19 Infection in Elderly Renal Dialysis Patients

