Each sample size calculation depends on the type of endpoints, the variability of data, analysis methods used, and the minimal difference (or effect size) that we wish to be able to detect between the treatment (with Zadaxin) or control (without Zadaxin) groups. There are four types of endpoints for this study, dichotomous (e.g., infection of COVID19, the primary endpoint; ICU admission; or mortality), polytomous (e.g., health changes: no change, moderate, severe changes), counts (e.g., occurrence of non-COVID-19 infections), or continuous outcome variables (e.g., CD4, CD8, CD4/CD8, length of hospital stay, recovery time from COVID19). For a dichotomous outcome, a suitable model is a logistic regression with the treatment status (treated or not treated with Zadaxin) as the primary covariate, demographic information (age, gender, race), health/medical information (e.g., Karnofsky score, co-morbidity, and other biomarkers) and environmental information (treatment center, among others) as other relevant covariates. Assume the infection rate for the control group is about 0.40 and with a significance level of 0.05 (unless specified otherwise), if we use a simple logistic regression, a sample of size 200 will be able to detect a change at least at 0.185 in the infection rates between the treatment and control groups with a power of 80%. If we have a bigger sample size, say 234, we would be able to detect a change with a minimal difference of 0.17 with the same power or a minimum difference of 0.185 with a power of 86.5%. Using more comprehensive procedures (below) or if the actual difference is (much) larger than the minimal difference, we will have a (much) higher power than 80% to detect the actual difference. If we make a conservative adjustment for multiple comparisons incorporating other covariates after a pre-screening step, at an adjusted significance level 0.005, a sample of size 205 will provide 80% power for detecting a change of at least as large as 0.23. Using a multiple logistic regression model that takes into account the correlation among the various covariates, say if the correlation is 0.2, we can detect a minimal difference at 0.202 with a sample size of 200. If the correlation is 0.5, the minimum detectable difference would be 0.25. The highly correlated covariates that lead to multicollinearity will indicate the need for removal of redundant covariates in modeling the endpoint, and the removal will lead to more degrees of freedom in our study and the same power in detecting the even smaller difference. We will use all the sample we have and incorporate censored data or treat missing information with survival or a more comprehensive model than the logistic regression; thus, we expect to be able to detect a smaller minimal difference or have a much higher power to detect the actual difference in the infection rates than given above.

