
For a continuous endpoint, with a sample size of 201, using the simplest testing procedure (with a possible transformation of the endpoint variable), we will be able to detect an effect size at least at 0.35 between the treatment and control groups with a power of 80%. Since we will use a general linear model to delineate the effects or variations due to covariates/factors, we expect to be able to detect a smaller minimal effect size or a higher power to detect the actual difference that is bigger than the minimal effect size. In a very conservative sense, comparing a polytomous response between treatment and control can be viewed as a multiple testing problem of comparing proportions for each of the categories. For response variables with three categories, if the proportion of a certain category is approximately 0.3, a sample of size 202 will enable us to detect a minimal change of 0.19 with a power of 80%. We emphasize that this calculation is very conservative, and we expect have much better performance, both in terms of detection of smaller departure and having better power. For the ordinal polytomus outcome, we are interested in

identifying if the treatment improves the proportion of different categories of the outcome than that of control. Assume that the response has 3 categories with equal proportion in the overall population (averaged over control and treatment). With a sample size of 200 we can detect a minimal improvement of size 0.725 in the overall odds ratio with 80% power. The count variables can be modeled as continuous with appropriate transformation and the sample size justification will be similar to that of a continuous response.

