15.2 Data analysis plan

The primary goal of the analysis is to study the effect of the treatment on the outcome variables, in consideration of other covariates, including the demographic information and medical history of the participants and dialysis centers, which can potentially interact with the treatment. First, we will do an exploratory analysis of all the covariates altogether and stratified in the treatment and control group. We will study the effect of each of these covariates separately and together on the outcome. In the comprehensive study of all factors, we will build several models, including both parametric and tree-based models. We will also consider relevant interaction between the independent variables in the model. For the parametric models, we will use logistic regression for the binary outcomes, general linear regression (after a possible transformation of some covariates) for the continuous outcomes, Poisson regression with an over-dispersion test or a general log-linear model, for count outcomes, and a multinomial regression for the categorical variables with more than two categories. We will assess the fitted models based on model diagnostics and goodness-of-fit/prediction measures, such as adjusted R^2 , AIC, BIC, and cross-validation. A follow-up analysis will be done based on the results obtained from the various regression models. All the significant first-order and interaction effects will be further analyzed to understand the nature of the effect, and possibly considering further models stratified by relevant covariates.

Interim analyses will be done at least in the interval of 1, 3, and 6 months for the purpose of monitoring, presentations to the monitoring board, and any remedies (as needed) to ensure the quality of the study and safeguard the study population.

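### Section 15.1 powers the ordered three-category outcome on one overall odds ratio, but 15.2 names only multinomial regression, for which power is about 70% rather than 80% if 0.725 is a log odds ratio

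*Combined protocol and SAP*

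**What the plan says.** Section 15.1 lists four endpoint types, one of them "polytomous (e.g., health changes: no change, moderate, severe changes". It then gives two separate calculations for outcomes with more than two categories.

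- The first compares arms one category at a time: a category proportion of about 0.3, a change of 0.19, 202 subjects and 80% power. The plan describes this calculation as conservative.
- The second is for ordered outcomes and is introduced by "For the ordinal polytomus outcome, we are interested in", followed by the aim of seeing whether treatment improves the distribution over the categories. Its assumption is "Assume that the response has 3 categories with equal proportion in the overall population (averaged over control and treatment", and its result is "With a sample size of 200 we can detect a minimal improvement of size 0.725 in the overall odds ratio with 80% power".

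Section 15.2 assigns a parametric model to each outcome type. For this type it is "a multinomial regression for the categorical variables with more than two categories". No ordinal, cumulative-logit or proportional-odds model is named, and ordered outcomes have no rule of their own.

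**The concern.** A single odds ratio across ordered categories is the parameter of a proportional-odds model, tested on 1 degree of freedom. A multinomial regression of a three-category outcome in its usual, nominal sense estimates two treatment coefficients and tests them jointly on 2 degrees of freedom. The power quoted in 15.1 for the ordered outcome therefore belongs to a different analysis from the one named in 15.2.

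Two things are at stake. The first is power: the extra degree of freedom is spent on departures that the ordered alternative does not predict. The second is interpretation. The multinomial test has no direction, so it can be significant when one arm merely has more subjects in the middle category and fewer in both outer ones. That does not answer the question of improvement posed in 15.1. The model also does not yield the one odds ratio on which the calculation is based.

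**Working it through.** **Inputs**

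- N = 200, effect 0.725, power 80% (section 15.1).
- Three categories, 1/3 each on average over the arms (15.1).
- Alpha: "with a significance level of 0.05 (unless specified otherwise" (15.1). Sidedness is not stated; two-sided is assumed.
- Allocation: "centrally randomized 1:1 to receive either no treatment or 1.6 mg Ta1" (10.5), so 100 per arm.
- Complete data: 240 enrolled, "anticipating that 40 subjects will drop off study for any of a number of reasons" (15.1), which leaves 240 − 40 = 200.

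**Step 1: reproduce the plan's figure.** The Whitehead proportional-odds formula for 1:1 allocation is

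N = 12 (z₀.₉₇₅ + z₀.₈₀)² / [(log OR)² (1 − Σp̄³)], with Σp̄³ = 3 × (1/3)³ = 1/9.

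With 0.725 as the log odds ratio (OR = 2.06, or 0.48 in the other direction):

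- N = 12 × 7.849 / (0.5256 × 0.8889) = 201.6, against the stated 200.
- Power at 200 = Φ(0.725 × √(200 × 0.8889 / 12) − 1.960) = Φ(0.83) = 79.7%, against the stated 80%.

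Other readings checked do not reproduce it:

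| Reading of 0.725 | N for 80% | Power at N = 200 |
|---|---|---|
| log OR, two-sided | 201.6 | 79.7% |
| log OR, one-sided 0.05 | 159 | 87.4% |
| OR = 0.725, two-sided | 1,025 | 23.5% |
| OR = 1.725, two-sided | 356 | 55.5% |

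**Step 2: category probabilities.** Choosing the cumulative-logit cut points so that the average over arms is 1/3 in each category, a log odds ratio of 0.725 gives 0.254 / 0.333 / 0.413 in one arm and 0.413 / 0.333 / 0.254 in the other.

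**Step 3: power of the joint 2-df test at N = 200.** Power is the upper tail of a noncentral chi-square with 2 df beyond the 5% critical value. The noncentrality can be obtained in three ways:

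- Whitehead: 200 × 0.8889 / 12 × 0.725² = 7.79, power 70.5%.
- Likelihood ratio, 2 × 100 × Σ[C ln(C/M) + T ln(T/M)], where C and T are the arm probabilities and M their mean: 7.64, power 69.6%.
- Pearson: 100 × 4 × 0.0794² / 0.3333 = 7.56, power 69.2%.

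In 100,000 simulated trials with 100 per arm, the multinomial likelihood-ratio test rejected in 70.0% (5.2% under the null). The ordinal score test (tie-corrected Wilcoxon) rejected in 78.9% (5.0% under the null).

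**Step 4: what would restore 80%.** The 2-df test needs a noncentrality of 9.63.

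- Sample size: 200 × 9.63 / 7.79 ≈ 247, up to 200 × 9.63 / 7.56 ≈ 255.
- Effect at N = 200: 0.725 × √(9.63 / 7.79) ≈ 0.81 on the log scale.

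**Step 5: sensitivity.**

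- All 240 analysed: ordinal power about 86%, 2-df power about 77% to 79%.
- 0.725 read as an odds ratio (log OR −0.322), N = 200: ordinal about 23.5%, 2-df about 18%.

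**The case against.** The best defence is that 15.1 does not rest outcomes of this type on an ordinal model alone. Its category-by-category calculation (0.3, change 0.19, N = 202) is nominal in spirit and closer to a multinomial regression. That is correct, and a reader should not infer that 15.1 has only an ordinal basis. But comparing one category at a time is not the joint treatment test, and 15.1 gives the ordinal calculation separately, with no named method in 15.2 to match it.

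Section 15.2 also promises several models, assessed by diagnostics, AIC, BIC and cross-validation, and some authors use multinomial loosely to include cumulative-logit models. This makes a fixed 2-df test less than certain. It does not settle the matter: no ordinal model is named, and choosing one later on fit criteria would not be pre-specification. If a cumulative-logit model is meant, the text should say so.

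A reader might also infer that 15.1 declares health change to be ordinal. It does not. It calls that example polytomous, and the sentence on ordinal outcomes names no endpoint. The order is a reasonable inference from the labels. Section 8.2 defines no three-category endpoint; the nearest item, change in comorbidities (number 8 of 11), has no such scale. Likewise, 15.1 never names proportional odds; the assumption is implied by its single odds ratio.

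Finally, this is a self-described pilot with a binary primary endpoint, so the consequence is limited. That stands.

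**Conclusion.** The mismatch is real: the power for the ordered outcome rests on one overall odds ratio, and the named analysis does not estimate one. The loss is about 9 to 10 percentage points, from about 79–80% to about 70%. This rests on five assumptions: 0.725 is a log odds ratio, the test is two-sided at 0.05, treatment is tested jointly on 2 df, there is no covariate adjustment (although 15.2 plans covariates), and 200 subjects are analysed under proportional odds.

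It is tempting to say flatly that the planned analysis has 70% power. The documents do not support that without these conditions, because 15.1 labels 0.725 as an odds ratio and 15.2 does not specify the treatment test. On the literal odds-ratio reading, the stated 80% fails mainly for another reason, and the model costs about 5 points (23.5% to 18%). The direction of the loss is the same on both readings.

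The point concerns a secondary-type outcome. It changes neither the primary analysis nor the enrolment target, but it should be corrected.

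**What to change.** In 15.2, name proportional-odds (cumulative-logit) regression for ordered outcomes with more than two categories, reporting one treatment odds ratio with its confidence interval. Keep multinomial regression for unordered outcomes, and as a sensitivity analysis where proportional odds is doubtful. In 15.1, state whether 0.725 is a log odds ratio and which outcomes are treated as ordered.

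Alternatively, if multinomial regression is to remain the analysis for ordered outcomes, restate the 15.1 power as about 70% under the conditions above.

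The first option costs one sentence in 15.2 and a clarification in 15.1, with no added subjects, visits or data. Its small downside is reliance on the proportional-odds assumption, which the single odds ratio in 15.1 already implies.

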16 ETHICS

16.1 Good Clinical Practice

The Investigator will ensure that this study is conducted in full compliance with the principles of the Declaration of Helsinki (as amended in Edinburgh, Tokyo, Venice, Hong Kong, and South Africa), ICH guidelines, in particular ICH GCP E6, and with the laws and regulations of the United States. Because this study is conducted under a U.S. IND, the Investigator will ensure adherence to the basic principles of Good Clinical Practice, as outlined, for example, in 21 CFR §312.50 and 312.56.

16.2 Institutional Review Board

The protocol and ICF for this study must be reviewed and approved by an appropriate IRB before subjects are randomized into the study. It is the responsibility of the Investigator to assure that all aspects of the institutional review are conducted in accordance with the requirements of all regulatory authorities.

16.3 Subject Information and Informed Consent

In accordance with regulatory and local ethics committee requirements, before study procedures are performed, subjects will be informed about the study and required to sign the IRB-approved ICF along with authorization to collect protected health information under HIPAA. This form will be signed after adequate explanation of the aims, methods, objective and potential hazards of the study and prior to undertaking any study-related procedures. Informed consent will be obtained according to the applicable IRB requirements. No subject is to be screened or treated until an ICF has been obtained. The signed ICF will be retained with the study records. Each subject will also be given a copy of his or her signed ICF at the screening visit.

16.4 Financial Disclosure by Investigators

Since this is a “covered” clinical trial, the Investigator will ensure that 21 CFR §54 is adhered to. A “covered” clinical trial is any study of a study drug or device in humans submitted in a marketing application or reclassification petition subject to this part that the applicant or the FDA relies on to establish that the product is effective (including studies that show equivalence to an effective product) or that make a significant contribution to the demonstration of safety. This requires that Investigators (inclusive of family members) provide documentation of their financial interest or proprietary interests in the study drug being studied. This documentation must be provided prior to the participation of the Investigator.

16.5 Archiving and Data Retention

According to 21 CFR §312.57, an Investigator shall retain adequate records for the study including copies of each subject’s CRFs, medical records, laboratory reports, ICFs, study drug accountability records, safety reports, information regarding subjects who were withdrawn and any other pertinent data. All records are to be retained by the Investigator for a period of 2 years following the date a marketing application is approved for the study drug for the indication for which it is being investigated or if no application is to be filed or if the application is not approved for such indication, until 2 years after the investigation is discontinued and the FDA is notified. The records will be available for copying and inspection if requested by regulatory authorities.

If the responsible Investigator retires, relocates or for other reasons withdraws from the responsibility of keeping records, custody must be transferred to a person who will accept the responsibility.

16.6 Confidentiality

The Investigator must assure that subjects’ anonymity will be strictly maintained and that their identities are protected from unauthorized parties.

The Investigator must keep a screening log showing names and addresses for all screened subjects and all subjects randomized into the trial.

³Clinical and research labs – please refer to the Study Procedures section (Serum will be cryopreserved until completion of study and assays run once serologic assay is available for COVID-19)

⁴Respiratory virus symptom inventory to include the description of cough, fever, shortness of breath, malaise, sore throat occurring over the prior week. If any are present, the information will be brought to the attention of PI or CoI.

⁵Signs and symptoms correlating with pre-existing or newly developed comorbidities will be inventoried.

⁶Ta1 will be administered twice weekly on dialysis days immediately upon completion of dialysis, with at least two full days between treatments.

18 APPENDIX 1

Respiratory Symptom Inventory

Symptom	Screen	W1	W2	W3	W4	W5	W6	W7	W8	M3	M4	M5	M6
Cough													
Fever >100.4													
Shortness of breath													
Sore throat													
Gastrointestinal symptoms													
Malaise													
Headache													
Muscle pain													
Loss of taste and/or smell													
Other (describe)
